- Hypotension.
- Biological abnormality such as hyponatremia, hyperkalemia, renal salt loss and hypoglycemia.

If an acute adrenal insufficiency is suspected, an extra visit will be performed in emergency and if the acute adrenal insufficiency is confirmed, the patient will be hospitalized to be treated at the choice of the investigator. If the serum cortisol dosage confirms clinical adrenal insufficiency, an open hydrocortisone therapy by hydrocortisone 20mg/d will be started and an appointment with the endocrinologist will be made. If the serum dosage does not confirm adrenal insufficiency, hydrocortisone will be stopped and other causes of the symptoms will be investigated. If no severe concomitant disease is found, the patient will be able to go back to her/his step of the protocol.

All clinical adrenal insufficiency reports will be reviewed by an independent committee to decide whether, according to the report, the diagnosis of clinical adrenal insufficiency can be validated and recorded for the study. This will be declared as a serious adverse event.

It is expected that less than 1% of patients in this study will experience clinical adrenal insufficiency.

3. Proportion of patients with biological adrenal insufficiency.

Two blood tests will be scheduled with a Synacthène® test at 4 and 7 months. A pathological Synacthène® test will be diagnosed if one hour after Synacthène®, serum cortisol is below 200 ng/mL or 600 nmol/L, or 20 µg/100 ml. In case of abnormal test at the latest Synacthène® test another Synacthène® test will be realized at M12.

4. Proportion of patients who needed a short rescue GC treatment during the protocol.
5. Proportion of patients who needed a GC intra-articular or peri-articular injection during the protocol related to the RA.
6. Proportion of patients with a flare confirmed by the clinician. In case of symptoms of flare, the patient will have an extra visit at her/his center. For DAS28 >3.2, a flare will be confirmed. A flare will be also diagnosed if the DAS28 is >3.2 at any scheduled visits.
7. The area under the curves of the self-administered Flare Assessment in Rheumatoid Arthritis (FLARE) questionnaire. FLARE is an approved self-assessment questionnaire that will be completed at each visit and in case of FLARE at home by the patient. The results are expressed as continuous data. The area under the curve of all the questionnaires will be the variable analyzed.

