34	Collection of consent (yes/no)	From the variable Date of signing of free and informed consent [CRF p9], the variable “Collection of consent” will take the value: " If yes : 
 • Consent signature date = not missing " Not if : 
 • Consent signature date = missing
35	Number of prednisone capsules consumed per level at M4 and M7	From the variables Prednisone bottle: Number of units reported and Prednisone bottle: Number of units given during the previous visit , the variable “ Number of prednisone capsules consumed at level 1 ” will take the value: Corresponding to the subtraction between: The number of units given and the number of units reported at level 1 [CRF p 45 and 90] The variables Number of prednisone capsules consumed at level 2/3/4/5/6 and Number of hydrocortisone consumed at level 1/2/3/4/5/6 will be derived using the same methods.
36	Total number of prednisone capsules consumed at M4 and M7	From the variables Number of prednisone capsules consumed at level 1 / 2 / 3 , the variable “ Total number of capsules consumed at M4” will correspond to the sum of all the variables mentioned (i.e. the sum of the number of capsules consumed at level 1, 2 and 3). Total Number variable of prednisone capsules consumed at M7 will be derived using the same methods using the variables Number of prednisone capsules consumed at level 1/2/3 . Variables Total number of hydrocortisone capsules consumed at M4 and Total number of hydrocortisone capsules consumed at M7 will be derived using the same methods.
37	Patient with pathological Synacthen test at M4 / M7 / M9 / M12 / VA1 / VA2 (yes/no)	Given the significant number of concordance problems between the variable “ Cortisol 60 minutes after stimulation with 0.25 mg of Synacthen® ” and the binary variable “ Is the Synacthen test considered pathological? ”, we have chosen to derive a variable which will allow us to reclassify patients with a pathological test or not, depending on the quantitative value of the variable “ Cortisol 60 minutes after stimulation with 0.25 mg of Synacthen® ”. This variable will be derived as follows:

STAR – Statistical Analysis Plan
V3, June 2023

Page 26 of 96

[figure not shown]
No.	VARIABLE NAME	DERIVATIONS

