		
From the Cortisol variables 60 minutes after stimulation with 0.25 mg of Synacthène® in µg/100mL at M4 / M7 / M9 / M12 / VA1 and VA2 [CRF p60, p85, p102, p127, p144, p155], the variable “ Patient with pathological Synacthen test (yes/no) » [CRF p61, p86, p103, p128, p145, p156], will take the value:
 
" If yes :
 
 the value of the variable: Cortisol 60 minutes after stimulation with 0.25 mg of Synacthène® in µg/100mL is strictly less than 20 µg/100mL. 
" Not if :
 
 the value of the variable: Cortisol 60 minutes after stimulation with 0.25 mg of Synacthène® in µg/100mL is greater than or equal to 20 µg/100mL. 
variables with pathological Synacthen test at M7 / M9 / M12 / VA1 / VA2 to M4 will be derived according to the same methods.
 
Due to concordance problems, for the analysis we will base ourselves on this derived variable and not on the CRF variable” [CRF p61, p86, p103, p128, p145, p156].

39	Additional visit 1 carried out (yes/no)	
From the variable Date of visit for VA1 [CRF p135], the variable “ Additional visit 1 carried out ” will take the value:
 
" If yes :
 
 The date of the visit is not missing 
" Not if :
 
 No if the visit date is missing 
The variable Additional visit 2 carried out (yes/no) will be derived using the same methods from the variable Date of visit for VA1 [CRF p146]

40	Follow-up duration (months)	
From the variables “ Date of inclusion visit ” [CRFp9] and “ Date of end of study ” [CRFp157], we will calculate the number of days elapsed between these two dates, divided by 30.4375 to obtain a duration in months .

STAR – Statistical Analysis Plan
V3, June 2023

Page 27 of 96

DATA ANALYSIS AT INCLUSION

1) Flowchart

STAR – Statistical Analysis Plan
V3, June 2023

Page 28 of 96

2) Descriptive analyses : descriptive tables at inclusion

A descriptive analysis of the explanatory variables will be carried out before any other analysis. Descriptive characteristics of patients included in this study will be described for the entire population and by strategy group separately.

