You felt a greater need for help for several days in a row due to your polyarthritis

Synacthen test at M4, M7, M9, M12, VAdd 1, VAdd 2

- Test carried out (yes/no) [CRF p60, p85, p102, p127, p144, p155]
 - If Yes, specify:
 - Cortisol without stimulation (yes/no) [CRF p60, p85, p102, p127, p144, p155]
 - Test value (µg/100mL) [CRF p60, p85, p102, p127, p144, p155]
 - Cortisol 60 minutes after stimulation with 0.25 mg of Synacthène® (yes/no) [CRF p60, p85, p102, p127, p144, p155]
 - Test value (µg/100mL) [CRF p60, p85, p102, p127, p144, p155]
 - Is the Synacthen test considered pathological? (yes /no) [Derived variable]
 - If No, if cortisol at 60 minutes is normal and the patient is on open-label hydrocortisone, specify:
 - Maintenance of hydrocortisone, specify dosage (mg/day) (yes/no) [CRF p61, p86, p103, p128, p145, p156]
 - If Yes, specify why
 - Hydrocortisone withdrawal (yes/no) [CRF p61, p86, p103, p128, p145, p156]
 - Other, specify (yes/no) [CRF p61, p86, p103, p128, p145, p156]
 - Accuracy (listing) [CRF p61, p86, p103, p128, p145, p156]
 - If Yes, is the patient summoned again for the introduction of hydrocortisone in accordance with the protocol? (yes /no) [CRF p61, p86, p103, p128, p145, p156]
 -]If No, another attitude is adopted towards the results of a pathological Synacthen test, please specify:
 - The patient was already on Hydrocortisone before this visit (yes/no) [CRF p61, p86, p103, p128, p145, p156]
 - Other, specify (yes/no) [CRF p61, p86, p103, p128, p145, p156]
 - Accuracy (listing) [CRF p61, p86, p103, p128, p145, p156]

STAR – Statistical Analysis Plan
V3, June 2023

Page 54 of 96

We will identify discordant patients, that is to say, those having a pathological test after recalculation [derived variable] although they were declared as normal in the eCRF, as well as patients who did not receive a open-label hydrocortisone until the next visit as planned in the protocol (patients to be classified in the protocol deviation group).

STAR – Statistical Analysis Plan
V3, June 2023

Page 55 of 96

End of study sheet

- Follow-up duration variable] [Derived
- Did the patient complete the trial according to protocol? (yes /no) [CRF p157]
 - Specify the reason for premature termination:
 - Adverse event or serious adverse event (yes/no) [CRF p157]
 - Resumption of RA activity/prescription of long-term prednisone or prednisolone (yes/no) [CRF p157]
 - Patient's refusal to prosecute (yes/no) [CRF p157]

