
Presence of biological adrenal insufficiency at one year (yes/no)
	
From the variables “ Test performed (Synacthen test) (yes/no) ” at M12 [CRFp127], “ Is the Synacthen test considered pathological? (yes /no) ” to M12 [Derived variable], “ Has hydrocortisone treatment been received in addition to the protocol since the last consultation? » and “ Biological signs of chronic adrenal insufficiency ” [CRFp111], we define 2 modalities:
 
" If yes :
 
 • “ Test carried out (Synacthen test) ” = Yes • AND “ Is the Synacthen test considered pathological? » = Yes 
OR
 
 • “ Has hydrocortisone treatment been received in addition to the protocol since the last consultation? » = Yes • AND “ Biological signs of chronic adrenal insufficiency ” = Yes 
" Not if :
 
 • “ Test carried out (Synacthen test) ” = No • AND “ Has hydrocortisone treatment been received in addition to the protocol since the last consultation? » = No 
OR
 
 • OR if “ Test carried out (Synacthen test) ” = Yes • AND “ Is the Synacthen test considered pathological? » = No • AND “ Has hydrocortisone treatment been received in addition to the protocol since the last consultation? » = No

STAR – Statistical Analysis Plan
V3, June 2023

Page 68 of 96

4) Proportion of Patients Needing Supplemental Prednisone to Control Flares

Proportion of patients who required salvage GC treatment during the protocol.

To meet this secondary endpoint, we will use the Treatment Compliance Variables at M4, M7, M9, M12, Vadd 1 and Vadd2 which will be combined to create a new binary derived variable as presented below :

Variable name	Derivation

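### Variable 37 settles every Synacthen disagreement in favour of the cortisol number, and tests declared pathological with a value of 20 or more are recoded without review

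*SAP*

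**What the plan says.** In the SAP's table of variables of interest, no. 37 (pathological Synacthen test at M4, M7, M9, M12 and the two additional visits) starts from a known data problem: "Given the significant number of concordance problems between the variable" holding the 60-minute cortisol and the site's yes/no verdict. The cause is not stated. The test is then reclassified from the number alone. It is pathological if the value "is strictly less than 20 µg/100mL" and not pathological otherwise. The site verdict is set aside: "Due to concordance problems, for the analysis we will base ourselves on this derived variable and not on the CRF variable".

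The diagnostic definition (section 8, secondary endpoint 3, repeated in the analysis of that endpoint) gives the cut-off in three units: "serum cortisol is below 200 ng/mL or 600 nmol/L, or 20 µg/100 ml". The CRF listing for the Synacthen test shows one numeric field per measurement, labelled in µg/100 mL, and no unit field.

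The same listing ends with the only planned identification of discordant tests: "those having a pathological test after recalculation [derived variable] although they were declared as normal in the eCRF", together with patients who did not receive open-label hydrocortisone as planned. Tests that disagree the other way are not mentioned.

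**The concern.** When two recorded items disagree for an unknown reason, always keeping the same one is safe only if the other is always at fault. The SAP does not argue this. It defines a pathological test by a numeric threshold, which is a good reason to prefer the number when the number is right. It is no reason to trust a number that may have been entered wrongly.

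The listing also looks in one direction only. A test that the site called pathological, with a recorded value of 20 or more, is changed to not pathological and nobody is asked to look at it. One plausible route to that pattern follows from the SAP's own definition. A centre whose laboratory reports in ng/mL or nmol/L could judge the result correctly against the cut-off for its unit, then type the figure unconverted into the µg/100 mL field. The verdict would be right, the number wrong, and the rule would keep the number. At stake is a possible understatement of pathological tests in the Synacthen tables and in part of secondary endpoint 3.

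**Working it through.** **Inputs.** From the SAP: cut-offs of 200 ng/mL, 600 nmol/L and 20 µg/100 mL (section 8, secondary endpoint 3); the rule that a value below 20 is pathological and 20 or more is not (variable 37). Not in the SAP, assumed: molar mass of cortisol 362.46 g/mol (range tried 362 to 363).

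**1. The SAP's equivalences.**
- 1 µg/100 mL = 10 ng/mL, so 20 µg/100 mL = 200 ng/mL. This reproduces.
- The SAP's own ratio for nmol/L is 600 / 20 = 30 per µg/100 mL.
- With the assumed molar mass, the factor is 10,000 / 362.46 = 27.6, so 20 µg/100 mL is about 552 nmol/L (551 to 552 over the range tried) and 600 nmol/L is about 21.7 µg/100 mL. On that assumption the nmol/L cut-off does not match the other two.

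**2. What an unconverted entry does under the rule.** The recorded number is the true value times the factor. A pathological test stays pathological only if true value × factor < 20.

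| Unit typed | Factor | Stays pathological if true value is below | Recoded as not pathological |
|---|---|---|---|
| ng/mL | 10 | 20 / 10 = 2.0 µg/100 mL | 2.0 to <20 |
| nmol/L, SAP ratio | 30 | 20 / 30 = 0.67 | 0.67 to <20 |
| nmol/L, assumed molar mass | 27.6 | 20 / 27.6 = 0.72 | 0.72 to <20 |

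Example: a true 15 µg/100 mL typed as 150 (ng/mL) or 450 (nmol/L, SAP ratio) reads as at least 20 and is coded not pathological.

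**3. The reverse direction.** A true value of 20 or more multiplied by 10, 27.6 or 30 is still 20 or more. Over true values from 0.05 to 60 µg/100 mL, no normal test became pathological for any of the three factors. For these two units the error runs one way.

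**4. The same pattern without an entry error.** On the assumed molar mass, a result between about 552 and 600 nmol/L is pathological by the nmol/L cut-off but becomes 20.0 to 21.7 after correct conversion, so the rule codes it not pathological. The stated cut-offs need to be reconciled; which one should stand is not a matter for this review.

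**5. Where a recoded test ends up.** Secondary endpoint 3 uses only the M12 value of variable 37, and joins it by OR to a second limb (added hydrocortisone together with biological signs of chronic adrenal insufficiency). For an M12 test wrongly recoded as not pathological:

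| Added hydrocortisone at M12 | Biological signs as reason | Result under the SAP |
|---|---|---|
| Yes | Yes | Yes (unchanged, through the second limb) |
| No | – | No (the positive is lost) |
| Yes | No | Meets neither the Yes nor the No definition |

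Only the last two rows are affected. In the primary endpoint, Modality 4 is built from the M12 hydrocortisone questions and does not use variable 37.

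**6. Missing number.** The rule has two branches, below 20 and at least 20. A test with a site verdict but no 60-minute value is assigned to neither.

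**The case against.** The strongest reply is that the cause is supposed, not documented. Both the CRF field and the rule name µg/100 mL, the three units belong to a diagnostic definition and are not a choice of entry unit, and the one discordance the SAP describes is the opposite of what a unit error would leave. Unit queries and range checks are ordinary data-management work, the SAP precedes the freeze, and a 150 or 450 in a µg/100 mL field is conspicuous. Applying the defined threshold uniformly is itself a defensible way to implement the endpoint.

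Most of this stands. The SAP does not show that unit errors occurred, and checks outside it cannot be excluded. What it does not answer is that the written rule overwrites disagreements the SAP itself calls numerous, without asking which item is wrong, and identifies only one of the two directions. For errors in capsule counts, by contrast, the SAP describes blinded patient-by-patient review (per-protocol population).

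A reader might go further in four ways that the document does not support:
- That a given share of pathological tests is lost. Assuming that 5 to 20% of tests carry another unit simply returns about 5 to 20% of pathological tests; the SAP gives no rate, and the second limb of endpoint 3 prevents that share from carrying over to the endpoint.
- That treated patients are wrongly sent to the deviation group. The listing takes tests derived as pathological but declared normal, so the cases at issue are missed by it, not placed on it.
- That power falls. No test is stated for endpoint 3.
- That errors can never run the other way. This holds for unconverted ng/mL or nmol/L entries only; dividing by 10 a value already in µg/100 mL would turn a normal test pathological.

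**Conclusion.** The point holds as a cheap improvement. Variable 37 resolves every disagreement in favour of the number without a stated reason, and tests declared pathological with a value of 20 or more are recoded without review. An unconverted entry in either of the other units the SAP names would produce that pattern for true values from 2.0 (ng/mL) or about 0.7 (nmol/L) up to 20 µg/100 mL, and would not produce the reverse. That such entries exist is an assumption.

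The reach is limited: the Synacthen descriptions at each visit, and the M12 test limb of secondary endpoint 3, mainly in patients with no added hydrocortisone recorded for biological signs. The primary endpoint is not touched, and no numerical size can be given from the document.

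**What to change.** Amend variable 37 so that, before the database freeze and blinded to arm:
- discordant tests are listed in both directions, together with values implausible in µg/100 mL;
- value and unit are checked against the laboratory report for the listed tests, and converted where needed;
- the existing cut-off is then applied to the checked value.

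Report endpoint 3 a second time with the CRF verdict in place of the derived variable. This sensitivity analysis also covers tests with a verdict but no usable number, and discordances that come from the three stated cut-offs and not from an entry error. Those cut-offs should be reconciled in the text.

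The cost is a set of data queries limited to the listed tests, and one extra table. No clinical rule changes.
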